## 1. INTRODUCTION

The following Statistical Analysis Plan (SAP) provides the outline for the statistical analysis of data collected from the EP-547-101 study (Protocol Original dated 17 June 2020).

The planned analyses identified in this SAP may be included in clinical study reports (CSRs), regulatory submissions, or future manuscripts. Also, post hoc exploratory analyses not necessarily identified in this SAP may be performed to further examine study data. Any post hoc, or unplanned, exploratory analyses performed will be clearly identified as such in the final CSR.

This amendment to SAP is done to incorporate the changes made to the study as per the various revisions of protocol:

- Protocol Amendment 1.0 dated 14 December 2020
- Protocol Amendment 2.0 dated 19 February 2021
- Protocol Addendum 1.0 to Amendment 2.0 dated 19 March 2021

## 2. PROJECT OVERVIEW

[figure not shown]
### 2.1.1 Study Design

This study is a first-in-human, Phase 1, randomized, single and multiple ascending dose (SAD and MAD) study with EP547 in healthy subjects and subjects with cholestatic or uremic pruritus. As shown in [Figure 1](#), each population will include a SAD or single dose (SD) segment followed by a MAD segment for a total of 6 segments (single ascending dose – healthy subject [SAD-HS] and multiple ascending dose – healthy subject [MAD-HS] in healthy subjects [HS]; single dose – cholestatic pruritus [SD-CP] and multiple ascending dose - cholestatic pruritus [MAD-CP] in subjects with cholestatic pruritus [CP]; and single dose - uremic pruritus [SD-UP] and multiple ascending dose - uremic pruritus [MAD-UP] in subjects with uremic pruritus [UP]. Each segment will evaluate at least 1 dose level. Pruritus is not a mandatory requirement for participation in SD-CP or SD-UP.

Although SAD-HS and all of the MAD segments will be conducted in a blinded manner (ie, subjects, Investigator, study-site personnel, and Contract Research Organization [CRO] staff not involved in PK sample analysis or regulatory reporting will be blinded to treatment), the Sponsor, including the Sponsor Medical Monitor, will be unblinded to treatment assignment to assess safety on an ongoing basis.

SAD-HS will evaluate at least 5 dose levels of EP547, establish the highest well-tolerated dose in healthy subjects, and guide MAD dosing in the same population. Evaluation of the first of 3 dose levels for MAD-HS may commence after 3 dose levels from SAD-HS have been fully evaluated by the Safety Review Team. When the results of all dose levels from the SAD-HS segment have been fully evaluated by the Safety Review Team, evaluation of a single dose level for SD-CP and SD-UP may commence. SD-CP and SD-UP will confirm predicted PK concentrations and guide MAD dosing in their respective populations. SD-CP and SD-UP may be conducted in parallel. Evaluation of at least 1 dose level for MAD-CP and MAD-UP may commence when the dose level from the SD segment specific to their population has been fully evaluated by the Safety Review Team. Subjects from the SD-CP and SD-UP segments may screen to determine eligibility for participation in the MAD segment specific to their population.

**Figure 1: EP-547-101 Study Designs**

### 2.1.2 Food effect (FE) Sub study

Twelve healthy subjects will participate in this 2-period, unblinded, randomized, crossover food effect sub study to evaluate the PK of a single dose of EP547 administered orally (PO) in a fasted or fed condition. Subjects who participated in SAD-HS or MAD-HS may not participate in FE-HS. Subjects will be randomized in a 1:1 ratio to either Sequence 1 (Fasted for FE Period 1, Fed for FE Period 2) or Sequence 2 (Fed for FE Period 1, Fasted for FE Period 2). The dose level to be tested in FE-HS will be 75 mg, which was selected based on safety and tolerability data and EP547 PK characteristics from SAD-HS and MAD-HS, and from data generated by nonclinical studies.

Doses between the 2 FE Periods must be separated by a minimum of 10 days to allow for washout of study drug.

**Fasted Regimen:**

EP547 will be administered after an overnight fast for a minimum of 8 hours. Subjects will remain fasted until after the 4-hour PK blood sample is collected.

[figure not shown]
**Fed Regimen:**

Subjects will fast overnight for a minimum of 8 hours. Approximately 30 minutes before administration of study drug, subjects will consume a high fat/high calorie breakfast and will be instructed to consume the entire meal in 30 minutes or less. Subjects must consume at least 90% of their meal to be eligible for dosing. The start and stop time and percentage of the breakfast consumed will be recorded. Per guidance from the Food and Drug Administration (FDA), the high fat/high calorie meal should derive approximately 150, 250, and 500 to 600 calories from protein, carbohydrate, and fat, respectively (FDA 2002). No other food or drink (other than water as specified above) will be permitted until after the 4-hour PK blood sample is collected.

**Both Regimens:**

Each meal and/or snack served at the clinic will be standardized, similar in caloric content and composition (except for the high-fat/high calorie breakfast served as part of the fed regimen), and consumed at approximately the same time in each FE Period during confinement.

**Figure 2: FE Study design**

PO = oral

Shading represents the mandatory period when subjects will be confined to the study site.

Visit 5 (Day 8) is also the Follow-Up visit and is to occur 7 days after the last administration of study drug.

## 2.2 Objectives

### 2.2.1 Primary objective

- The primary objective of this study is to evaluate the safety and tolerability of single and multiple ascending doses of EP547 in healthy subjects and subjects with cholestatic or uremic pruritus

### 2.2.2 Secondary objectives

The secondary objectives of this study are:

- To evaluate the pharmacokinetics (PK) of single and multiple ascending doses of EP547 in healthy subjects and subjects with cholestatic or uremic pruritus
- To assess QT/corrected QT (QTc) interval prolongation risk using EP547 concentration-QT/QTc modeling in healthy subjects (for use at a later development stage, not as a result of a safety signal)

[REDACTED]

### 2.3 Endpoints

#### 2.3.1 Primary endpoints

- Adverse events (AEs)
- Clinical laboratory assessments
- Vital signs and body weight
- Standard 12-lead Electrocardiogram (ECGs)
- Physical examinations

#### 2.3.2 Secondary endpoints

- Plasma EP547 and metabolites (as applicable) concentrations
- Plasma PK parameter estimated using noncompartmental analysis (NCA), as appropriate:
  - SAD segments:  $C_{max}$ ,  $t_{max}$ ,  $K_{el}$ ,  $t_{1/2}$ ,  $AUC_{\infty}$ ,  $AUC_t$ ,  $\%AUC_{extra}$ ,  $CL/F$ , and  $Vz/F$
  - MAD segments:  $C_{max}$ ,  $C_{trough}$ ,  $t_{max}$ ,  $K_{el}$ ,  $t_{1/2}$ ,  $AUC_t$  (as appropriate),  $AUC_t$ ,  $CL/F$ ,  $Vz/F$ , and  $R_{ss}$
- Urine PK parameters estimated using NCA, as appropriate:
  - SAD-HS segment:  $A_e$ ,  $Fe$ ,  $CLr$
- Skin EP547 and metabolites (as applicable) concentrations
- Holter monitoring for 12-lead ECG acquisition and subsequent cardiodynamic analysis

[REDACTED]

- [REDACTED]
- [REDACTED]
- [REDACTED]
- [REDACTED]
- Plasma PK parameter estimated using noncompartmental analysis (NCA) for the FE segment, as appropriate:
  - $C_{max}$ ,  $t_{max}$ ,  $K_{el}$ ,  $t_{1/2}$ ,  $AUC_{\infty}$ ,  $AUC_t$ ,  $\%AUC_{extra}$ ,  $CL/F$ , and  $Vz/F$

## 2.4 Sample Size

No formal sample size calculation has been made. The sample size has been selected to provide adequate information on safety, tolerability, PK, and PD following single and multiple doses of EP547.

80 to 132 subjects are expected to participate in the study, including 64 to 72 healthy subjects, 8 to 30 CP subjects, and 8 to 30 UP subjects:

- 5 to 6 groups of 8 subjects each in SAD-HS
- 3 groups of 8 subjects each in MAD-HS
- 1 group of 6 subjects each in SD-CP and SD-UP (non-randomised)
- 1 to 2 groups of 8 to 12 subjects each in MAD-CP and MAD-UP; up to 6 subjects each from the SD-CP and SD-UP segments will participate in the MAD segment specific to their population if they meet the requirement for pruritus (will be rescreened and allocated a new participant ID following washout)

For FE sub study a sample size of 12 subjects was selected to estimate the effect of food on the PK of EP547.

## 2.5 Randomization

SAD-HS and all of the MAD segments will be conducted in a blinded manner (i.e., subjects, Investigator, study-site personnel, and Contract Research Organization staff not involved in PK sample analysis or regulatory reporting will be blinded to treatment). The Sponsor, including the Sponsor Medical Monitor, will be unblinded to treatment assignment to assess safety on an ongoing basis.

SD-UP and SD-CP will be open label, with all subjects assigned active treatment (EP547) and do not require randomization.

FE sub study will be open label and randomized.

Furnished below are the details of randomisation in each segment.

- SAD-HS:
  - Up to 5 dose levels (with the flexibility to evaluate a sixth level)
  - 8 participants per group, randomized EP547: Placebo 3:1
  - Sentinel dosing - sentinels randomised EP547: Placebo 1:1
  - Non-sentinel dosing randomised EP547: Placebo 5:1
- MAD-HS:
  - Up to 3 dose levels
  - 8 participants per group, randomized to receive EP547 or placebo for 7 days in a 3:1 ratio
  - No sentinel dosing
- SD-CP/UP:

- Initiated after all dose levels of SAD-HS have been fully evaluated by the Safety Review Team
  - No randomization, unblinded, 1 dose level each (SD-CP and SD-UP), 6 participants per group
- MAD-CP:
  - 1 dose level (with potential 2nd cohort if required)
  - 8 participants, randomized to receive EP547 or placebo for 7 days in a 3:1 ratio
  - Potential to enroll up to 4 more subjects (for a total of 12)
  - No sentinel dosing
- MAD-UP:
  - 1 dose level (with potential 2nd cohort if required)
  - 8 participants, randomized to receive EP547 or placebo for 7 days in a 3:1 ratio
  - Potential to enroll up to 4 more subjects (for a total of 12)
  - No sentinel dosing
- FE:
  - Single dose of EP547 administered orally (PO) in a fasted or fed condition
  - 12 participants, randomized to one of the two sequence in 1:1 ratio  
[Sequence 1 (Fasted for FE Period 1, Fed for FE Period 2) or Sequence 2 (Fed for FE Period 1, Fasted for FE Period 2)]

### 3. STATISTICAL CONSIDERATIONS

Data will be handled and processed per the sponsor's representative (Novotech) Standard Operating Procedures (SOPs), which are written based on the principles of good clinical practice (GCP).

Each study segment (SAD-HS, MAD-HS, SD-CP/UP, MAD-CP/UP, FE) will be presented separately for tables. Listing will include all data separated by segment and dose level (if applicable). For FE segment separate listing will be provided. Novotech will not be responsible to generate any figures for the study.

#### 3.1 General Considerations

All data collected on the electronic case report form (eCRF) will be presented in the data listings and will be listed and sorted by treatment group, participant number and visit, where applicable. All descriptive summaries will be presented by treatment group and nominal visit/time point (where applicable).

Unless otherwise stated, the following methods will be applied:

- Continuous variables: Descriptive statistics will include the number of non-missing values (n), arithmetic mean, standard deviation (SD), median, minimum and maximum values.

The minimum and maximum values will be displayed to the same decimal precision as the source data, the arithmetic mean, SD and median values will be displayed to one more decimal than the source data for the specific variable.

The appropriate precision for derived variables will be determined based on the precision of the data on which the derivations are based, and statistics will be presented in accordance with the above mentioned rules.

- PK data: The actual blood sampling dates and times relative to dosing time will be listed by treatment group, participant and nominal sampling time, with time deviation calculated, for all participants with available plasma concentration data, including participants excluded from the PK population. Individual (for each participant) and mean plasma and skin EP547 and metabolites (as applicable) concentrations over time will be displayed graphically in linear and semi-logarithmic plots of concentrations versus time. The actual collection time will be used for individual plasma and skin EP547 and metabolites (as applicable) concentration curves and the nominal time will be used for the plots of mean concentration curves.

For plasma and skin PK concentration data, the number of non-missing values, number of below limit of quantification (BLQ) values, arithmetic mean, standard deviation, median, minimum, maximum, coefficient of variation (CV%), geometric mean, geometric standard deviation (SD) and geometric coefficient of variation (geo CV%) values will be presented. For the calculation of summary statistics, unrounded data will be used and reported to three significant figures with the exception of n, n BLQ, and CV% which will be presented to the nearest integer and one decimal place, respectively.

For PK parameter data, the number of non-missing values, arithmetic mean, standard deviation, geometric mean, geometric SD, geometric CV, median, minimum and maximum values will be presented. Individual PK parameters will be presented to three significant figures with the exception of  $T_{max}$  which will be presented to two decimal places.

- Categorical variables: Descriptive statistics will include counts and percentages per category. The denominator in all percentage calculations will be the number of participants in the relevant analysis population with non-missing data, unless specifically stated otherwise. Percentages will be displayed to one decimal place. Proportions will be displayed to 3 decimal places.
- Repeat/unscheduled assessments: Only values collected at scheduled study visits/time points will be presented in summary tables. If a repeat assessment was performed, the result from the original assessment will be presented as the result at the specific visit/time point. All collected data will be included in the data listings.

- Assessment windows: All assessments will be included in the data listings and no visit windows will be applied to exclude assessments that were performed outside of the protocol specified procedure windows.
- Result display convention: Results will be center aligned in all summary tables and listings. Participant identifiers visit and parameter labels may be left-aligned if required.
- Date and time display conventions: The following display conventions will be applied in all outputs where dates and/or times are displayed:

Date only: YYYY-MM-DD

Date and time: YYYY-MM-DD HH:MM

If only partial information is available, unknown components of the date or time will be presented as 'NK' (not known), i.e., '2016-NK-NK'. Times will be reported in military time.

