9.4.2.4. Early Study Termination Visit

Subjects who discontinue from the study early should have the Early Study Termination Visit conducted as soon as possible after the last dose of study drug, ideally within 2 days after the last dose of study drug. Subjects are to arrive at the clinic after an overnight fast (at least 8 hours) and will undergo the following assessments during the Early Study Termination Visit:

- [REDACTED]
- [REDACTED]
- [REDACTED]
- Complete physical examination
- Vital signs
- Standard 12-lead ECG
- Body weight
- Laboratory assessments:
 - Serum pregnancy test (females only)
 - Chemistry and hematology
 - Urinalysis (MAD-HS and MAD-CP only)
- Assessment of concomitant medication usage
- Assessment of AEs

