### 3.2 Key Definitions

The following definitions will be used:

- Baseline: The baseline value is defined as the last available valid (quantifiable continuous or categorical value), non-missing observation for each participant prior to first study drug administration. Repeat and unscheduled assessments will be included in the derivation of the baseline values. [REDACTED]
- For FE Segment ([REDACTED]) the baseline value is defined as the last available valid (quantifiable continuous or categorical value), non-missing observation for each participant prior to the study drug administration in each period. Repeat and unscheduled assessments will be included in the derivation of the baseline values. Below table provide the baseline measurement to be considered for each parameter.

Measurement	Period 1	Period 2
Laboratory(Hematology, Chemistry & Urinalysis), Vital Signs and ECG	Pre-dose value captured at Visit 2 Day 1, if missing then value captured at Screening.	Pre-dose value captured at Visit 4 Day 1.

- Change from Baseline: The change from baseline value is defined as the difference between the result collected/derived at a post-baseline visit/time point and the baseline value.

The change from baseline value at each post-baseline visit/time point will be calculated for all continuous parameters using the following formula:

$$\text{Change from Baseline Value} = \text{Result at Visit/Time Point} - \text{Baseline Value}$$

The change from baseline value will only be calculated if the specific post-baseline visit/time point result and the baseline value for the parameter are both available and will be treated as missing otherwise.

- Percent Change from Baseline

Percent Change from Baseline at each post-baseline visit/time point will be calculated for all continuous parameters using following formula.

$$\% \text{ Change from Baseline} = 100 \times [(\text{Post-Dose Visit Value} - \text{Baseline}) / \text{Baseline}]$$

- Study Day: The study day of an event is defined as the relative day of the event starting with the date of the first study drug administration (reference date) as Day 1 (there will be no Day 0).

The study day of events occurring before the first study drug administration will be calculated as:

$$\text{Study Day} = (\text{Date of Event} - \text{Date of First Study Drug Administration})$$

For events occurring on or after Day 1, study day will be calculated as:

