#### **13.2 Safety Laboratory Assessments**

Blood and urine samples will be collected at the time points specified in the Schedule of Events (refer to the Protocol) to conduct hematology/coagulation, chemistry and urinalysis (including microscopic examinations) analyses.

The following tests will be performed within each of the specified test panels:

Hematology:

- Basophils
- Eosinophils
- Hematocrit
- Hemoglobin
- Lymphocytes
- Monocytes
- MPV
- Neutrophils
- Platelets
- Red blood cells (erythrocytes) (RBC)
- White blood cells (leukocytes) (WBC) (total and differential)

Chemistry:

- Albumin
- Alkaline Phosphatase (ALP)

- Alanine aminotransferase (ALT)
- Aspartate aminotransferase (AST)
- Bicarbonate
- Bile acids
- Blood Urea Nitrogen (BUN)
- Corrected Calcium
- Calcium
- Chloride
- Creatinine
- Creatine phosphokinase (CPK)
- Direct Bilirubin
- Gamma-glutamyltransferase (GGT)
- High-Density Lipoprotein cholesterol (HDL-c)
- Lactate Dehydrogenase (LDH)
- Low-Density Lipoprotein cholesterol (LDL-c)
- Magnesium
- Phosphate
- Potassium
- Sodium
- Triglycerides
- Total Bilirubin
- Total Cholesterol
- Total Protein
- Urea

Urinalysis (Dipstick) & Microscopic Urinalysis:

- Bilirubin
- Blood
- Color
- Glucose
- Ketones
- Leukocytes
- Nitrite
- pH
- Protein
- Specific Gravity
- Urobilinogen

- Microscopic Examinations (listing only)

All laboratory data collected at scheduled and unscheduled visits will be included in the listings, but only results collected as scheduled visits will be included in the summary tables.

Results for individual parameters may be reported in different units depending on the analyzing laboratory. If required, the results (and the corresponding normal range cut-off values) for individual parameters may be converted to International System of Units (S.I.) to summarize the data. Parameters will be presented in both units (S.I and conventional units) in the listing.

For all the parameters where a unit value has been reported, the parameter names that will be used in the outputs will comprise of the test name and the unit of measure, for example, 'Albumin (g/L)'. For the urinalysis parameters, the parameter name will be the reported test name only. Parameters will be sorted alphabetically within tables and listings.

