For all parameters where a normal range limit value was reported, the normal range will be derived based on the available lower and upper limit values and any reported mathematical symbols. If both a lower and upper limit value is available, the normal range will be presented as '(Lower, Upper)'.

The reported results for each parameter with a defined normal range will be classified ('Low', 'Normal', 'High') in relation to the defined normal range limits. If a result is equal to the normal range cut-off value, the result will be considered 'Normal'.

The hematology, chemistry and urinalysis results tables will present summary statistics for each laboratory parameter within the specific test panel. For each parameter, summaries will be presented for the baseline and each scheduled post-baseline visit. In addition, summaries will be presented for the change from baseline values at each scheduled post-baseline visit (continuous descriptive analysis).

The decimal precision to which the summaries for each parameter will be based on the maximum number of decimals to which the reported result or the normal range limits are presented to in the raw data. The results and normal ranges will be displayed to the same decimal precision in the listings.

The hematology and chemistry result with values out of normal range will present counts and percentages for the reported results at baseline and each post-baseline visit/time point. Result categories will be ordered as 'Low', 'Normal' and 'High' (categorical descriptive analysis).

Additionally, counts (%) of number participants with normal and abnormal CS/NCS at each scheduled time point will also be presented along with shift tables that will represent the changes in normal categories across post-baseline time points (categorical descriptive analysis).

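### Summary tables use scheduled time points only, so a laboratory or ECG abnormality seen only at an unscheduled or repeat assessment enters no out-of-range or shift table

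*SAP*

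**What the plan says.** The general rule in SAP 3.1 is: "Only values collected at scheduled study visits/time points will be presented in summary tables". For repeats it adds: "If a repeat assessment was performed, the result from the original assessment will be presented as the result at the specific visit/time point". Everything else goes to the listings: "All collected data will be included in the data listings". Section 13.2 restates the restriction for the laboratory ("only results collected as scheduled visits will be included in the summary tables"), and 13.3 and 13.4 do the same for vital signs and ECGs.

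The categorical safety tables are built by time point. On out-of-range results, 13.2 says: "The hematology and chemistry result with values out of normal range will present counts and percentages for the reported results at baseline and each post-baseline" visit or time point. Counts of normal and abnormal results, split by clinical significance, and the shift tables also run over time points. The ECG shift table in 13.4 covers the overall interpretation only. Vital signs have summary statistics and change from baseline, with no shift or out-of-range table.

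The denominator rule in 3.1 is: "The denominator in all percentage calculations will be the number of participants in the relevant analysis population with non-missing data". Before dosing, unscheduled values do count; SAP 3.2 says: "Repeat and unscheduled assessments will be included in the derivation of the baseline values".

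**The concern.** Laboratory assessments and standard ECGs are primary outcomes (Protocol 15.2.1, SAP 2.3.1). Protocol 15.4 says that changes in them will be compared across dose levels, where applicable, and with placebo. A reader makes that comparison from the shift and out-of-range tables. If an abnormality shows only at an unscheduled draw, the subject is counted as normal at every scheduled time point and the dose level looks clean.

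The scheduled assessments leave gaps in which an unscheduled test is the only laboratory or ECG observation. In small dose groups, one missed subject is a large share of the group.

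**Working it through.** The plan states no figure for this point, and no sample size or power calculation, so there is nothing to reproduce. The check compares the tabulation rule with the schedule, then sizes one event.

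**1. Which tables are affected.** From SAP 13.2 to 13.4 and the table list in SAP 18:
- Laboratory out-of-range: 14.3.4.x.2, where x = 1 hematology, 2 chemistry, 3 urinalysis. (The list includes urinalysis, although the text of 13.2 names only the other two.)
- Laboratory shift: 14.3.4.x.3.
- ECG interpretation shift: 14.3.5.3.
- Vital signs: only 14.3.5.1, values and change from baseline, so there is no categorical table to be missing from.

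No readable title or text in these sections describes a worst or any-time post-baseline summary.

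**2. Where an unscheduled result is the only observation.**
- MAD chemistry and hematology after the first dose: Days 2, 4, 8, 14 and 21 (Protocol 9.4.2.2 and 9.4.2.3). If the Day 4 sample is taken predose, as Appendix B indicates where applicable, the four doses of Days 4 to 7 fall between two draws.
- MAD standard ECG after the first dose: 3 hours on Day 1, predose on Day 3, and Day 8 (Protocol 11.8). None is scheduled on Days 4 to 7.

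**3. Size of one event in a dose-level column.** Let n be the number of EP547 subjects in the column, one of whom has an abnormality seen only off schedule.
- True share = 1/n.
- Tabulated share = 0/n if that subject's scheduled values are normal, or 0/(n − 1) if the subject has no value at that visit, because only non-missing values enter the denominator.
- Healthy-subject level, n = 6 (Protocol 7.1.1): 1/6 = 16.7%, shown as 0/6 or 0/5.
- MAD-CP or MAD-UP level enlarged to 12 at 3:1, n = 12 × 3/4 = 9: 1/9 = 11.1%, shown as 0/9 or 0/8.

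**4. Size in the pooled columns of SAP 3.7.1.**
- Overall EP547 in SAD-HS: 5 × 6 = 30 gives 1/30 = 3.3%; 6 × 6 = 36 gives 1/36 = 2.8%.
- Overall EP547 in MAD-HS: 3 × 6 = 18 gives 1/18 = 5.6%.
- Pooled placebo in SAD-HS: 5 × 2 = 10 gives 1/10 = 10.0%; 6 × 2 = 12 gives 1/12 = 8.3%.

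**5. Frequency.** The documents give no rate. Under assumed per-subject rates p from 2% to 20%, the chance of at least one such subject among 6 is 1 − (1 − p)^6, which runs from 11.4% to 73.8%. That width shows only that the documents cannot settle how often this would happen.

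**6. What the repeat rule does.** If the original is normal and the repeat abnormal, the abnormal result is not tabulated. If the original is abnormal and the repeat normal, the abnormal result stays in the table. The rule loses information in one direction only.

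**The case against.** The strongest reply is that abnormalities that matter reach tables by another route. Protocol 11.1.1 allows a clinically significant laboratory, ECG or vital-sign result to be an adverse event. Protocol 11.1.4.1 gives four alternative triggers for laboratory values and vital signs, including a result that forces a change or stop of study drug, or extra testing beyond a repeat. Those events appear in the TEAE tables, by maximum severity and by treatment withdrawal. Escalation relies on individual data reviewed by the Safety Review Team (Protocol 7.1, 7.3.3). Comparisons with placebo are described as qualitative (Protocol 15.8). The food-effect addendum reports that all doses tested to date were well tolerated, with no safety signals identified.

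Much of this stands: no dosing decision rests on these tables, and listings for about 6 subjects per level can be read. But TEAE tables show terms and severity, not a shift category; a diagnosis replaces the laboratory term where one is known; results judged not clinically significant are not to be reported as adverse events under 11.1.1; and the triggers in 11.1.4.1 do not name ECGs. Listings do not themselves make the comparison in Protocol 15.4.

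A reader might infer more than the documents support:
- **That early-termination results are excluded.** The protocol plans that visit ("Subjects who discontinue from the study early should have the Early Study Termination Visit conducted") and gives it a column in Appendices A and B, the schedules from which SAP 13.2 to 13.4 take their time points. The plain reading is that it is scheduled. The SAP is silent only on how it is displayed.
- **That the rule removes the Day 8 value of a subject who stops early.** That value is absent under any by-visit table, and such subjects still have follow-up about 1 week, and in MAD about 2 weeks, after the last dose (Protocol 8.4).
- **That peak values are lost from the shift tables.** Those tables hold categories. A higher unscheduled value does not change a result already classed as High.
- **That the baseline rule distorts the comparison.** Day 1 predose values are scheduled, so an unscheduled value sets baseline only if it is taken after that assessment and before dosing, or if the scheduled one is missing. It could move baseline either way.

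**Conclusion.** The point holds in a narrow form. An abnormal laboratory category or ECG interpretation seen only at an unscheduled or repeat post-dose assessment is absent from every out-of-range and shift table, for any subject and not only those who stop drug. One such EP547 subject in a healthy-subject dose level is 16.7% of the group and is shown as 0%.

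This rests on two conditions: the subject's scheduled values are in the normal category, and no redacted output supplies the missing summary. It does not rest on any assumed rate. It does not show that early-termination data are dropped, that vital-sign tables are affected in the same way, or that escalation was misinformed. It is a worthwhile, inexpensive improvement to the reporting of primary safety outcomes, not a defect that undermines the analysis.

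**What to change.** In Tables 14.3.4.x.2, 14.3.4.x.3 and 14.3.5.3, add one worst-post-baseline row that uses all post-dose results (scheduled, repeat, unscheduled and early termination) against the same baseline. In the food-effect segment that is the period baseline already defined in SAP 3.2.

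Define worst in advance. For the out-of-range tables, count any post-baseline Low and any post-baseline High separately. For the shift tables, order the categories as normal, abnormal not clinically significant, abnormal clinically significant. Use as the denominator subjects with at least one post-dose result. Keep all by-visit summaries on scheduled values.

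The cost is a short addition to SAP 3.1 and one extra row per table. The data are already collected for the listings, and nothing changes in the conduct of the study. The drawback is uneven ascertainment: subjects tested more often have more chances to be abnormal. A footnote should say so.
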